10.3.4. Safety Analyses

Safety will be assessed by summarizing and analyzing AEs including adjudicated cerebrocardiovascular events, IBD events, laboratory analytes including neutrophil counts, QIDS-SR16, C-SSRS, and vital signs. The duration of treatment exposure will also be summarized.

Primary safety analyses will be based on the Randomized Withdrawal Safety Population in Period 2.

For combined Periods 1, 2, and 3, safety data will be summarized for the Lead-In Period Safety Population.

For Period 2, safety data will be summarized for the Randomized Withdrawal Safety Population. Treatment group comparisons will be performed on categorical safety data using Fisher's exact test as described in Section 10.3.1.2.1; continuous safety data will be analyzed by an ANCOVA model.

For Period 4 safety data will be summarized according to the treatment patients were on prior to entering Period 4.

The categorical safety measures will be summarized with incidence rates. The mean change of the continuous safety measures will be summarized by visits.

Further details will be described in the SAP.

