### ***6.1.3. General Considerations for Analyses during the Extension Period Including the Double-Blind RW Period (Period 2)***

#### **6.1.3.1. RW ITT and RW Safety Populations**

For patients who are randomized in Period 2 (group B), comparisons between Combined Ixekizumab treatment group and placebo, as well as between each ixekizumab regimen (80 mg Q2W or 80 mg Q4W) and placebo, will be performed for all analyses at each scheduled visit in Period 2 including Visit 515 at Week 64.

Period 2 starts at the first injection of study treatment after randomization (at Week 24) and ends at the following study events:

- Prior to the first injection of study treatment at Week 64 (Visit 515) for not retreated patients who have completed visit at Week 64. If injection at Week 64 is missing, the next injection date after Week 64 is used;
- Prior to the first injection of retreatment for patients who have been retreated within Period 2;
- ETV prior to Week 64.

For patients who are in the RW ITT Population and have been retreated with the ixekizumab treatment regimen due to a flare or any other reasons, only data prior to the time of the retreatment will be included in the analysis for Period 2. Data after retreatment will be imputed using nonresponder imputation (NRI) method for categorical variables and mBOCF method for continuous variables.

The observed values after retreatment will be used for other specified analysis, for example, efficacy analysis for Flare Population with Retreatment.

For efficacy and health outcomes, baseline is defined as the last available value before the first dose of study treatment in Period 2 from the originating study and, in most cases, will be the value recorded at Week 0 from the originating study.

The primary analysis method for treatment comparisons of categorical binary efficacy and health outcome variables will be a logistic regression with treatment group, geographic region, and originating study as factors using PROC Logistic with Wald method. The odds ratio and 95% CIs will be reported; treatment difference and 95% CI will also be reported. In the case when logistic regression model does not produce statistical results due to sparse data, Fisher's exact test will be used. Same analysis will also be carried out at each of other scheduled visits in Period 2.

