For safety analysis for the RW Safety Population, baseline is defined as the last nonmissing assessment prior to the first injection of study treatment in Period 2.

Fisher's exact test will be used for all adverse event (AE), discontinuation, and other categorical safety data. Continuous vital sign and laboratory values will be analyzed by an ANCOVA with treatment and baseline value in the model.

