### 6.13.1. Extent of Exposure

Duration of exposure to study drug will be summarized by treatment group for RW Safety population for Period 2 and Lead-In Period Safety Population for Combined Periods 1 and 2 and Combined Periods 1, 2, and 3 using descriptive statistics.

- The duration of exposure for RW Safety Population during Period 2 will be calculated as:

*Duration of exposure (days)*

$$= \text{Date of last visit (scheduled or unscheduled) in Period 2} \\ - \text{Date of first dose in Period 2} + 1$$

- The duration of exposure on ixekizumab for Lead-In Period Safety Population during Combined Periods 1 and 2 or Combined Periods 1, 2, and 3:

- For patients on uninterrupted ixekizumab treatment regimen during Combined Periods, it will be calculated as:

*Duration of exposure (days)*

$$= \text{Date of last visit (scheduled or unscheduled) in the Combined Periods} \\ - \text{Date of first dose in Periods 1} + 1$$

- For patients who are randomized to placebo at Week 24, ixekizumab exposure will be calculated as:

$$\text{Duration of exposure (days)} = \text{Duration 1} + \text{Duration 2},$$

where duration 1 = *Date of last visit in Period 1 – Date of first dose in Period 1* + 1 and duration 2 =

*Date of last visit on retreatment on ixekizumab in the combined periods – Date of first dose of retreatment on ixekizumab in the combined periods* + 1,

where duration 2 is a non-zero value for patients who are retreated with ixekizumab during the combined periods, and it is 0 for patients who are on placebo from Week 24 to the end of the combined periods.

The number and percentage of patients in each of the following categories will be included in the summaries:

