### 6.13.2. Adverse Events

Adverse events (AEs) will be classified based upon the latest version of the MedDRA. Adverse events will be recorded at every study visit. Any condition starting on or after the date of informed consent will be considered an AE. Any preexisting condition which worsens in severity on or after the date of informed consent will be considered and recorded as an AE on the *Adverse Event (AE)* eCRF page from the date of worsening onwards.

A treatment-emergent adverse event (TEAE) is defined as an event that first occurred or worsened in severity after baseline and on or prior to the date of the last visit within the defined treatment period. Both the date/time of the event and the date/time of the dose (that is, injection) are considered when determining TEAEs. Treatment-emergent AEs will be assigned to the study period to which it's considered treatment-emergent:

- The MedDRA lowest level term (LLT) will be used when classifying AEs as treatment-emergent.
- The maximum severity recorded for each LLT prior to the first dose date/time in the treatment Period will be used as the pre-treatment severity for that LLT. If an event during the baseline period has missing severity, and the event persists during the treatment period, then it will be considered as treatment-emergent, regardless of the postbaseline level of severity. Events with a missing severity during the treatment period will be considered as treatment-emergent.
- AEs with a particular LLT will be classified as treatment-emergent if they first start on or after the first dose date/time in the treatment period (ie, a patient has no preexisting conditions with that lowest level term), or if the severity is greater than the pre-treatment severity for that lowest level term. If a partial AE start date/time is present, the date/time will be compared as far as possible to the treatment start date/time in order to determine whether the event is treatment-emergent or not. If there is any doubt, the event will be flagged as treatment-emergent.

A follow-up emergent adverse event (FEAE) is defined as an event that first occurred or worsened in severity after the date of Visit 14 (Group A) or Visit 519 (Group B) (that is, Week 104) or the ETV:

- The MedDRA LLT will be used when classifying AEs as follow-up emergent.

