- For AEs that are ongoing at the date of Visit in Week 104 or ETV, the maximum severity recorded for each LLT on or prior to the date of the Visit at Week 104 or ETV will be used as the follow-up baseline severity for that LLT.

If a partial or completely missing AE start date/time or end date/time is present, the following imputation rules will be utilized in the analysis:

- For the start date:
  - If year, month, and day are missing, then use the earlier of the patient's first visit date or the consent date.
  - If either month or month and day are missing, then use January 1.
  - If only day is missing, impute the first day of the month.
- For the start time:
  - Impose as 23:59
- For the end date:
  - If year, month, and day are missing, then use the patient's last visit date in the follow-up period.
  - If either month or month and day are missing, then use December 31.
  - If only day is missing, then use the last day of the month.
  - The imputed date will not be beyond the patient's last visit date in the follow-up period.
- For the end time:
  - Impose as 23:59.

- If there is any doubt, the event will be flagged as treatment-emergent or follow-up emergent according to the corresponding study period. If a follow-up emergent event is already counted as treatment-emergent during the prior treatment period, it will not be counted as a follow-up emergent event.

Adverse events and TEAEs will be summarized for the following study periods by treatment groups (see [Table RHBY.6.1](#)) and analysis populations, treatment comparisons between treatment groups in Period 2 will be conducted using a Fisher's exact test:

- Combined Periods 1 and 2, Combined Periods 1, 2, and 3 (Lead-In Period Safety Population)
- Period 2 (RW Safety Population).

The following summaries/analyses will be performed:

- An overall summary of AEs including the number and percentage of patients who experienced TEAE, TEAE by maximum severity, death, SAE, TEAE possibly related to study treatment occurring in  $\geq 5\%$  of patients in the total ixekizumab group, SAE judged by investigator as possibly study treatment related (for combined periods only), discontinuations from the treatment due to an AE, and TEAEs of special interest.
- TEAE by SOC and PT.
- TEAE by maximum severity, SOC, and PT.

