The overall summary of AEs will also be provided for the RW Safety Population during Period 3, Long-Term Ixekizumab Treatment Efficacy Population and Ixekizumab Structure Population by treatment groups.

Follow-up emergent adverse events will be summarized for the Follow-Up Period Population for Period 4:

- FEAEE by PT.

In general, for all AE-related summaries, the number and percentage of patients experiencing the events will be presented by treatment group. In general, events will be ordered by decreasing frequency in the Combined Ixekizumab group, followed in the order of ixekizumab Q2W, ixekizumab Q4W, and placebo (when applicable) group, within SOC and/or PT for sorting.

A by-patient listing of all AEs will be provided.

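### Period 2 adverse events are compared as crude percentages although retreatment shortens placebo observation, and the Period 3 placebo column can hold patients already back on ixekizumab

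*SAP*

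**What the plan says.** **Period 2.** Protocol 10.3.4 states: "Primary safety analyses will be based on the Randomized Withdrawal Safety Population in Period 2". SAP 6.1.3.1, whose heading covers both the RW ITT and RW Safety Populations, ends the period at this point for retreated patients: "Prior to the first injection of retreatment for patients who have been retreated within Period 2". SAP 6.13.2 defines a treatment-emergent event as one that "first occurred or worsened in severity after baseline and on or prior to the date of the last visit within the defined treatment period". For adverse event summaries, "the number and percentage of patients experiencing the events will be presented by treatment group", and "treatment comparisons between treatment groups in Period 2 will be conducted using a" Fisher's exact test. Section 6.1.3.1 says the same, that Fisher's "exact test will be used for all adverse event (AE), discontinuation, and other categorical safety data".

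Exposure is reported. SAP 6.13.1 says "Duration of exposure to study drug will be summarized by treatment group for RW Safety population for Period 2", and total patient-years are tabulated. The only between-arm event comparison that uses exposure is the Poisson regression for uveitis in Table RHBY.6.5.

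**Period 3.** SAP 6.13.2 adds: "The overall summary of AEs will also be provided for the RW Safety Population during Period 3". SAP 6.1.1 analyses this population by assigned treatment. SAP 6.1.5 and 6.1.5.2 set no cut at retreatment. Table RHBY.6.1 gives the population a placebo column but no placebo-then-ixekizumab column, although the Flare Population has one. Period 3 compliance (SAP 6.8) uses the same groups. The same table row lists comparisons with placebo for Periods 2 and 3, while 6.1.5.2 rules out inferential statistics in Period 3.

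**The concern.** Cutting Period 2 at retreatment is right in itself, because it keeps ixekizumab events out of the placebo arm. But the cut falls mainly on placebo. A percentage of patients with an event depends on how long they were watched, so an arm watched for less time shows fewer affected patients at the same underlying rate. The protocol's primary safety comparison could then show an apparent excess of common events on ixekizumab that reflects follow-up only.

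In Period 3 the issue is labelling. Events that occur on retreatment ixekizumab could be displayed under placebo.

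**Working it through.** **Inputs from the documents.** About 200 patients at 2:1, so 133 ixekizumab and 67 placebo; flares 10% and 70% (SAP 5.2). Period 2 lasts 40 weeks (SAP 5.1). Group B visits are 4-weekly (Protocol Section 2). A flare needs two consecutive visits at ASDAS 2.1 or above, or one visit above 3.5 (Protocol 5.1). Retreatment begins at the next scheduled visit (Protocol 7.4).

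**Plan's own figure.** Exact enumeration of the two-sided Fisher test for 10% v 70% gives power above 99.9% at 133:67, consistent with the stated figure of over 99%.

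**Assumed, because not in the documents.** Flare timing and event rates. Event times are exponential with the same rate λ in both arms and independent of flare. There is no other dropout. A flare is detected at the next 4-weekly visit but not before Week 32, and retreatment follows 4 weeks later. Observed time T = min(retreatment time, 40 weeks). The expected crude percentage is the mean of 1 − exp(−λT/52.18), with λ per patient-year. Over a full 40 weeks at λ = 1.0 this is 1 − exp(−40/52.18) = 53.5%; at 0.5 it is 31.8% and at 0.1 it is 7.4%.

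**Results at 70% v 10% flares** (weeks counted from Week 24):

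| Flare timing | Mean weeks, ixekizumab v placebo | Ratio | Crude % at λ = 1.0 | Fisher p<0.05 at λ = 1.0 / 0.5 / 0.1 |
|---|---|---|---|---|
| Constant hazard from week 0 | 38.6 v 27.8 | 1.39 | 52.0 v 39.8 | 33% / 19% / 4% |
| Constant hazard from week 12 | 39.1 v 32.3 | 1.21 | 52.6 v 45.5 | 13% / 8% / 4% |
| Constant hazard from week 20 | 39.5 v 35.6 | 1.11 | 53.1 v 49.2 | 6% / 5% / 3% |
| Uniform over weeks 20-40 | 39.5 v 36.6 | 1.08 | 53.1 v 50.3 | 5% / 5% / 3% |

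With equal follow-up the test's actual size is about 4% for a 50% event. At λ = 0.1 the test is not inflated, but the crude risk ratio still tracks the exposure ratio (1.21 to 1.38 in the first two rows).

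Patient-years in the first row: 133 × 38.56 / 52.18 = 98.3 on ixekizumab and 67 × 27.80 / 52.18 = 35.7 on placebo. A rate using these denominators is equal in the two arms by construction.

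**Sensitivity.**
- Flares 50% v 20%, onset weeks 0 to 12: exposure ratio 1.09 to 1.16, rejection about 5.5 to 9.5% at λ = 1.0.
- Flares 30% v 10%: ratio 1.05 to 1.09, rejection about 4 to 6%.
- Earlier flares go the other way. With all flares in weeks 4 to 20, retreatment 4 weeks later and no Week 32 floor, observation is 37.6 v 23.2 weeks (ratio 1.62) and rejection is about 54% for an event with 50% risk over 40 weeks.
- The Week 32 floor is a simplification. SAP 6.10.1 drops Week 24 (V505) from the statistical flare endpoint only; V505 counts for retreatment in the IWRS, so detection at Week 28 is possible. Allowing Week 28 detection for every patient moves the first row's ratio only from 1.39 to 1.41, and the SAP expects a high Week 24 score to be very rare.

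**Check of the remedy.** A first-event rate ratio test rejects in 4.5 to 5.0% of trials at λ = 0.5 to 1.0. If a shared log-normal frailty (SD 0.3, 0.5 or 0.8) drives both flare and events, the rate ratio is 1.01-1.02, 1.01-1.05 or 1.03-1.11 instead of 1, against crude risk ratios of 1.16 to 1.52.

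**Period 3.** Under the table's timings, 42 to 62% of placebo-assigned patients (about 28 to 41 of 67) would be back on ixekizumab before Week 64.

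**The case against.** Several points on the other side stand.

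- Patient-years by arm are already planned, so an attentive reader can see the imbalance. These p-values lie outside the error-controlled family (SAP 6.5), and no decision rule depends on them.
- The bias runs against ixekizumab, so a reader who infers that the plan hides drug harm would be wrong.
- A reader might take 13 to 33% as the range of false positives. The documents do not support that. Protocol 5.4 sets 12 to 24 weeks of follow-up to cover clearance, about 5 half-lives, so late flares are plausible, and they remove almost all of the inflation.
- A reader might say that the SAP gives no Period 3 grouping rule. It does: assigned treatment, which read literally keeps retreated patients under placebo. A reader might also infer that retreatment events are never attributed to ixekizumab. They are, in the Lead-In Period Safety Population, where placebo time is excluded and the baseline for treatment-emergent events is reset at retreatment (SAP 6.1.1, 6.1.2.1, 6.13).
- Table RHBY.6.1 uses one merged row for both periods. The specific text in 6.1.5.2 governs, so Period 3 tests against placebo are not really planned.

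What remains is that no planned between-arm comparison, uveitis apart, corrects for unequal time at risk.

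**Conclusion.** The Period 2 point holds as a cheap improvement to the primary safety presentation. Placebo observation is shorter whenever flares are more frequent on placebo, and crude percentages then favour placebo at equal true rates. How far depends on flare timing and event frequency, neither of which the plan gives. The bias can be material for common events with early flares at 70% v 10%. It is slight with late flares or with 30% v 10%. For uncommon events the test is not inflated, although the crude ratio is still shifted. The figures also assume events independent of flare and no other dropout.

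In Period 3 the consequence is a labelling problem in a descriptive adverse event summary and a compliance table. It does not invalidate an inference.

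**What to change.** **Period 2 (SAP 6.13.2, 6.13.3 and Table RHBY.6.8).** Beside the crude percentages and Fisher's test, show patients with an event per 100 patient-years at risk by arm, with time at risk ending at the first event. For common events, add a rate ratio with a log time-at-risk offset, or a time-to-first-event comparison, with 95% CI. Keep Fisher's test for sparse events: at 0.05 per patient-year, 13 to 17% of simulated trials had an arm with no events.

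State two limits. Both additions assume that the cut at retreatment is not informative for adverse events. Early placebo time may also still carry residual ixekizumab: in the first two rows of the table, the first 12 weeks are 12/32.3 = 37% to 12/27.8 = 43% of placebo observation, against 12/38.6 = 31% on ixekizumab. A rate ratio does not remove this.

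**Period 3.** Define columns by the treatment being taken at the start of Period 3, show retreated placebo patients separately, and count events after a later retreatment under ixekizumab. Footnote Table RHBY.6.1 so that its comparisons apply to Period 2 only.

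**Cost.** SAP and table-shell wording plus modest programming from data already held; the exposure derivation in 6.13.1 needs a version ending at the first event. Patient-year rates assume a roughly constant rate, which time to first event avoids.

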### **6.1.3.2. Flare Population**

For patients who experienced a flare (Flare Population), a set of selected key efficacy outcomes at time of flare will be summarized.

For the Flare Population with Retreatment in Period 2, the period starts at the time of first injection of the retreatment of ixekizumab 80 mg Q2W or 80 mg Q4W following the flare and ends on the date of Period 2 defined in Section 6.1.3.1.

Summary statistics will be provided based on the Flare Population with Retreatment for a subset of efficacy outcomes: the proportion of patients who regain response in ASDAS <1.3, ASDAS <2.1, and who achieve/maintain an ASDAS<1.3, ASDAS<2.1, ASAS20, ASAS40, ASAS5/6, ASAS partial remission, ASDAS major improvement and clinically important improvement within 16 weeks after the ixekizumab retreatment for patients who have 16 weeks of retreatment. No inferential statistics will be provided. The Kaplan-Meier estimates of the proportion of patients who first regain response on the variables of interest will be carried out at each retreatment interval (4 weeks, 8 weeks, etc.) up to 40 weeks. If an ongoing patient has not regained response by 16 weeks or Week 64, the patient will be censored at 16 weeks and Week 64, respectively. For time to response through Week 64, if a patient discontinued the study prior to Week 64, the patient will be censored at the date of their last visit during Period 2.

For counting regaining a response, once a patient has a response, the status is cumulative and carried forward. This counting process starts at the first visit when the retreatment is initiated. For counting achieving/maintaining a response, the status may change with time and the status depends on the response at each visit and does not depend on the previous visit.

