7.4. Dosage Modification

As described in Section 5.1, if a patient who has achieved a state of sustained remission (Group B) during the randomized withdrawal-retreatment period experiences a flare and meets the criteria for retreatment, the patient will be retreated with the ixekizumab treatment regimen that he or she was receiving prior to withdrawal (ixekizumab 80 mg Q2W or ixekizumab 80 mg Q4W). During Period 2, retreatment will begin at the next scheduled visit. During Period 3, given the longer interval between visits, retreatment may begin at the next scheduled visit or at an unscheduled visit prior to the next scheduled visit.

As of Week 64, patients in Group A receiving ixekizumab 80 mg Q4W may have their dose escalated to ixekizumab 80 mg Q2W in Period 3 if the investigator determines that the patient may benefit from an increase in frequency of dosing to achieve adequate disease control. Dose escalation may begin at the next scheduled visit or at an unscheduled visit prior to the next scheduled visit.

As of Week 64, patients in Group B ([Table RHBY.3](#)):

- who are receiving placebo will remain on placebo, and will be monitored per the Schedule of Activities (Section 2) for eligibility (i.e., flare) to be retreated with the ixekizumab treatment regimen they were receiving prior to withdrawal (ixekizumab 80 mg Q2W or ixekizumab 80 mg Q4W).
- who are receiving ixekizumab 80 mg Q4W may have their dose escalated to ixekizumab 80 mg Q2W in Period 3 if the investigator determines that the patient may benefit from an increase in dosing to achieve adequate disease control. Escalation to ixekizumab 80 mg Q2W may occur only after the patient has been retreated upon flare with the ixekizumab treatment regimen received during Period 1 (ixekizumab 80 mg Q4W) for at least 12 weeks.
- who are receiving ixekizumab 80 mg Q2W will remain on this dose until completion of the study or early discontinuation.

Table RHY.3. Dosage Modification for Group B during Period 2 and Period 3

Period 1 (Open-Label)	Period 2 (Blinded)	Period 3 (Blinded)	If Flare during Period 2 or 3, Retreat (Open-Label)	12 Weeks after Retreat, Escalate (Period 3) (Open-Label)
ixekizumab 80 mg Q2W	ixekizumab 80 mg Q2W	ixekizumab 80 mg Q2W	ixekizumab 80 mg Q2W	N/A
	placebo	placebo	ixekizumab 80 mg Q2W	N/A
ixekizumab 80 mg Q4W	ixekizumab 80 mg Q4W	ixekizumab 80 mg Q4W	ixekizumab 80 mg Q4W	ixekizumab 80 mg Q2W
	placebo	placebo	ixekizumab 80 mg Q4W	ixekizumab 80 mg Q2W

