**Randomized Withdrawal (RW) Intent-to-Treat (ITT) Population:** Efficacy and health outcome analyses for Period 2 will be conducted on RW ITT Population, defined as all patients who achieved a state of sustained remission and were randomized to 40-week double-blind placebo-controlled RWR period (Group B), even if the patient does not receive the correct treatment or otherwise does not follow the protocol. Patients will be analyzed according to the treatment to which they are assigned.

**RW Safety Population:** Safety analyses will be conducted on the RW Safety Population, defined as all randomized patients in Group B who have received at least 1 dose of study

treatment after randomization in the specified period. Patients will be analyzed according to the treatment to which they are assigned.

**Flare Population:** Defined as all randomized patients in Group B who experience a flare after randomization at Week 24. Efficacy summaries will be conducted for Period 2 and Combined Periods 2 and 3 on the Flare Population who receive at least one injection of ixekizumab retreatment after flare in the Combined Periods 2 and 3. Patients will be analyzed according to the treatment to which they are assigned at randomization and the retreatment.

**Dose Escalation Population:** Exploratory efficacy summaries will be conducted for Period 3 on Dose Escalation Population, defined as all patients (from Group A and Group B) who have been treated ixekizumab 80 mg Q4W for at least 12 weeks, and had their dose escalated to ixekizumab 80 mg Q2W (determined by investigator).

**Follow-Up Period Population:** Safety analysis for Period 4 will be conducted on the Follow-Up Period Population, defined as all patients who have completed an originating study (RHBV, RHBW, or RHBX) through Week 52 and have entered the Post-Treatment Follow-Up Period (Period 4) in RHBY. Patients will be analyzed according to the treatment they are taking before entering Period 4.

[Table RHBY.6.1](#) displays analyses purpose and treatment groups for each analysis population and study period.

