**Table RHBY.6.1. Treatment Groups and Major Patient Populations for Analysis Periods for Study RHBY**

Population	Period	Analyses	Treatment Groups	Group Comparisons
Lead-In Period Safety Population	Combined Periods 1 & 2 Combined Periods 1, 2, & 3	Safety	IXE80Q2W IXE80Q4W Total IXE	Descriptive No inferential statistics
Long-Term Ixekizumab Treatment Efficacy Population	Combined Periods 1 & 2 Combined Periods 1, 2, & 3	Efficacy and health outcomes	IXE80Q2W a IXE80Q4W a Total IXE	Descriptive No inferential statistics
RW Safety Population	Period 2 Period 3	Safety	IXE80Q2W IXE80Q4W Total IXE Placebo	Total IXE vs. Placebo IXE80Q2W vs. Placebo IXE80Q4W vs. Placebo
RW ITT Population	Period 2 Combined Periods 2 & 3	Efficacy and health outcomes	IXE80Q2W IXE80Q4W Total IXE Placebo	Total IXE vs. Placebo IXE80Q2W vs. Placebo IXE80Q4W vs. Placebo
Ixekizumab Structure Population	At Week 56 for a 2-year assessment	Efficacy	IXE80Q2W IXE80Q4W Total IXE	Descriptive No inferential statistics
Flare Population with retreatment	Period 2, Combined Periods 2 and 3	Efficacy	PBO/IXE80Q2W PBO/IXE80Q4W PBO/IXE IXE80Q2W/IXE80Q2W IXE80Q4W/IXE80Q4W IXE/IXE	Descriptive No inferential statistics
Dose Escalation Population	Period 3	Efficacy	PBO/IXE80Q4W, IXE80Q4W/ IXE80Q4W Total	Descriptive No inferential statistics
Follow-Up Population	Period 4	Safety	IXE80Q2W IXE80Q4W Total IXE Placebo	Descriptive No inferential statistics

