	
Other secondary outcomes:
 
Treatment group by TE-ADA, NAb and Titer group on:
 
 
ASAS20,
 
ASAS40,
 
ASDAS <2.1
 
	
Descriptive statistics (observed):
 
Number and proportion of patients achieving response of interest.
 
No inferential statistics.
	
IXE80Q2W, IXE80Q4W, Total IXE by TE-ADA status, NAb status, and titer group, respectively. At Week 64 and Week 104

Flare Population with Retreatment (to assess the efficacy of retreatment)
	
For other secondary objectives:
 
 
ASAS20,
 
ASAS40,
 
ASAS5/6,
 
ASAS partial remission,
 
ASDAS:           
 
ASDAS<1.3
 
ASDAS<2.1
 
 
 
Clinically-important improvement
 
Major improvement,
 
Inactive disease
 
	
Descriptive statistics (for categorical variables) for within 16 weeks of ixekizumab retreatment.
 
Kaplan-Meier estimates of the proportion of patient who regain response on the variables of interest at each post-retreatment interval up to 40 weeks.
	
PBO/IXE80Q2W, PBO/IXE80Q4W PBO/IXE IXE80Q2W/ IXE80Q2W IXE80Q4W/ IXE80Q4W IXE/IXE
 
no inferential statistics within 16 weeks of Ixekizumab retreatment and at each retreatment interval (4 weeks, 8 weeks, etc.) up to 40 weeks.

Abbreviations: ASAS = Assessment of Spondyloarthritis International Society; ASDAS = Ankylosing Spondylitis Disease Activity Score; BASDAI = Bath Ankylosing Spondylitis Disease Activity Index; BASFI = Bath Ankylosing Spondylitis Functional Index; BASMI = Bath Ankylosing Spondylitis Metrology Index; Baseline=baseline from the originating study RHBV, RHBW or RHBX; CRP = C-reactive protein; ITT = intent-to-treat; IXE-Structure = patients from Ixekizumab Structure Population; IXE80Q2W = ixekizumab 80 mg every 2 weeks; IXE80Q4W = ixekizumab 80 mg every 4 weeks; MASES = Maastricht Ankylosing Spondylitis Enthesitis Score; mBOCF = modified baseline observation carried forward; MMRM = mixed model for repeated measures; mNRI = modified nonresponder imputation; NRI = nonresponder imputation; SJC = swollen joint count; TJC = tender joint count; Total IXE = IXE80Q2W and IXE80Q4W combined; RW = randomized withdrawal.

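### Applied to Combined Periods 2 and 3, as the SAP tables imply, the 4- and 8-week regained-response estimates are biased low, because retreatment starts at Weeks 64, 76 and 88 have no scheduled visit before 12 weeks

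*SAP*

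**What the plan says.** - SAP 6.1.3.2 lies in the section on Period 2. Its analysis period "ends on the date of Period 2 defined in Section 6.1.3.1". The Kaplan-Meier estimates of first regained response "will be carried out at each retreatment interval (4 weeks, 8 weeks, etc.) up to 40 weeks". The censoring rule is: "If an ongoing patient has not regained response by 16 weeks or Week 64, the patient will be censored at 16 weeks and Week 64". Regain is cumulative from the first responding visit; a separate achieve/maintain status is read visit by visit.
- SAP 6.1.1 goes further: "Efficacy summaries will be conducted for Period 2 and Combined Periods 2 and 3 on the Flare Population". Table RHBY.6.1 lists "Period 2, Combined Periods 2 and 3" for the retreated Flare Population.
- Table RHBY.6.5 gives that population the same grid with no period limit: "no inferential statistics within 16 weeks of Ixekizumab retreatment and at each retreatment interval (4 weeks, 8 weeks, etc.) up to 40 weeks".
- The protocol's Schedule of Activities has Group B visits every 4 weeks to Week 64, then at Weeks 76, 88, 100 and 104.
- Protocol 7.4 starts Period 2 retreatment at the next scheduled visit. For Period 3: "During Period 3, given the longer interval between visits, retreatment may begin at the next scheduled visit or at an unscheduled visit".
- SAP Table RHBY.6.4 dates a flare carried forward at a missed visit 28 days after the last visit in Period 2 but 84 days after it in Period 3. The SAP thus allows for the wider spacing when it dates flares. It has no matching rule for regain.

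**The concern.** A Kaplan-Meier curve of time to first observed response is right at a given week only if patients still at risk could have been seen by then. A patient retreated at Week 64 who responds after 3 weeks is first assessed at 12 weeks. Until then the curve carries that patient as a non-responder, so late starters pull the early part of the combined curve down whatever the drug does. The cumulative 16-week count has a related problem: more visits give more chances to record a response.

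What is at stake is the apparent speed of recapture after retreatment, and how the PBO/IXE and IXE/IXE columns look side by side if their flares fall at different times.

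**Working it through.** **1. The plan's own figure.** The documents give no size for the retreatment analysis. The only flare rates are in SAP 5.2: 10% on ixekizumab and 70% on placebo, with 200 patients randomized 2:1 (133 v 67). Exact enumeration of the 2-sided Fisher test at 0.05 gives power 0.9999999991, which reproduces the stated figure of over 99%.

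**2. Visit arithmetic.** Weeks from retreatment start to each later scheduled visit, up to 40 weeks:

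| Start week | Weeks to visits | Assessments within 16 weeks |
|---|---|---|
| 36 | 4, 8, 12, 16, 20, 24, 28, 40 | 4 |
| 48 | 4, 8, 12, 16, 28, 40 | 4 |
| 52 | 4, 8, 12, 24, 36 | 3 |
| 56 | 4, 8, 20, 32 | 2 |
| 60 | 4, 16, 28, 40 | 2 |
| 64 | 12, 24, 36, 40 | 1 |
| 76 | 12, 24, 28 | 1 |
| 88 | 12, 16 | 2 |
| 100 | 4 | 1 (study visits end at 4 weeks) |

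Three of the four scheduled starts from Week 64 on have nothing at 4 or 8 weeks. A Week 100 start, or an unscheduled start, can be seen sooner than 12 weeks.

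**3. How many flares are late (assumption: Period 2 hazards continue).**
- Period 2 flares: 67 × 0.7 = 46.9 on placebo; 133 × 0.1 = 13.3 on ixekizumab.
- Period 3 flares: 67 × 0.3 × 0.7 = 14.1; 133 × 0.9 × 0.1 = 12.0.
- Period 3 share: 14.1/61.0 = 23% (PBO/IXE); 12.0/25.3 = 47% (IXE/IXE); 26.0/86.2 = 30% overall.
- At half the hazard in both arms, the Period 3 risks are 1 − √0.3 = 0.452 and 1 − √0.9 = 0.051. The shares become 16%, 32% and 20%.

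Counted by retreatment start at Week 64 or later, the simulated shares are higher, at 26-31% (PBO/IXE) and 48-56% (IXE/IXE), because flares found late in Period 2 can start retreatment at Week 64 or later.

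**4. Effect on the curve.** This was simulated under assumptions that are not in the documents: constant flare hazards as above; exponential time to regain with a median of 4 or 8 weeks; retreatment at the detecting visit, at the next scheduled visit, or (Period 3 only) 2 weeks after detection; combined follow-up censored at Week 104. Ranges are over the three start rules. Entries are estimated regain at 4 / 8 / 12 weeks.

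| True regain | Period 2 only, censored Week 64 | Combined, PBO/IXE | Combined, IXE/IXE |
|---|---|---|---|
| 50 / 75 / 87.5% | about 50 / 75 / 87-88% | 37-40 / 54-57 / 84-85% | 29-35 / 40-48 / 83-85% |
| 29 / 50 / 65% | about 29-30 / 50-51 / 64-66% | 22-23 / 36-38 / 61-62% | 18-20 / 27-31 / 60-62% |

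Hand check at 4 weeks: the estimate is the true value × (1 − share of late starters with no visit by 8 weeks). With retreatment at the detecting visit, that share is 21.5% (PBO/IXE) and 35.4% (IXE/IXE). This gives 50% × 0.785 = 39.3% and 50% × 0.646 = 32.3%, against 39.2% and 32.4% simulated.

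**5. The 16-week count.** Suppose a 50% chance of response at any one visit (assumed). One look gives 50%. Four looks give between 50% (perfectly correlated visits) and 1 − 0.5⁴ = 94% (independent visits). With a 4-week correlation of 0.7, they give 77%.

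**6. Ordering of the columns.** If only the ixekizumab hazard falls in Period 3, the IXE/IXE late share drops from about 50% to 36% at half the hazard and to 25% at a quarter. The last is level with the 26% for placebo under the same start rule, and the ordering disappears.

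**The case against.** The strongest reply is that the grid was meant for Period 2 only. SAP 6.1.3.2 is a Period 2 subsection, censors at 16 weeks or Week 64, and stops at 40 weeks, which is the length of Period 2; a Week 32 start followed to Week 104 would have 72 weeks. The secondary objective concerns retreatment after a flare in Period 2. Protocol Table RHBY.5 calls the Periods 2 and 3 combined analysis exploratory, and the SAP's exploratory section is blacked out, so a separate rule may exist there. All of this stands, and it means the sentence in 6.1.3.2 is not itself at fault. It does not settle the matter. SAP 6.1.1 and Table RHBY.6.1 schedule the combined summaries, and Table RHBY.6.5, the only visible efficacy specification for this population, applies the grid without a period limit. A programmer following the visible text would reuse it.

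Three stronger readings are tempting, and the documents do not support them:
- A reader might infer that the Period 2 analysis is biased. It is not: 4-weekly visits with Week 64 censoring recover the true values.
- A reader might infer that IXE/IXE is necessarily hit harder. That needs ixekizumab-arm flares to fall later, and no Period 3 flare rate is given.
- A reader might compute 50% × (1 − 0.47) = 26% for IXE/IXE at 4 weeks. That treats every Period 3 flare as unseen at 4 weeks, although a Week 100 start has a visit then; the simulated range is 29-35%.

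It is also fair to say that the output is descriptive and that no test between the retreatment columns is planned.

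**Conclusion.** The point holds for Combined Periods 2 and 3 only. On the visible text, early regained response there is biased low. A true 50% at 4 weeks reads as about 29-40%, and a true 75% at 8 weeks as about 40-57%, across both columns and the three start rules. By 12 weeks most of the gap has closed (83-85% against 87.5%). The direction follows from the visit schedule. The size rests on constant flare hazards taken from the design rates and on an assumed speed of regain. A larger effect in IXE/IXE is conditional on later flares in that arm. The missing combined-period censoring rule is a gap in its own right. No primary or major secondary test is affected, so this is a cheap improvement to a descriptive analysis.

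**What to change.** - In Table RHBY.6.5, state that the 4- and 8-week Kaplan-Meier steps apply to retreatment started in Period 2, with follow-up censored at Week 64. The censoring matters because a Week 60 start has no 8-week visit.
- For Combined Periods 2 and 3, report regain separately for starts before Week 64 and from Week 64 on, with first reporting at 12 weeks for the latter. Alternatively, use an interval-censored (Turnbull) estimator with actual visit dates.
- State the Week 104 censoring rule for the combined analysis.
- Do not pool on response status at a 12-week visit: starts at Weeks 56, 60 and 100 have no scheduled visit 12 weeks later.
- Leave the Period 2 analysis unchanged.

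The cost is SAP wording and one split table, with no new data. The drawback is precision: on the design rates with equal hazards, only about 26 patients (14.1 + 12.0) would flare in Period 3, so late-start estimates would be imprecise.
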